Does an information leaflet provide an effective way of communication in the peri-procedure period? Will it help in better information delivery and hence reduce the number of avoidable postponements and delay. And does this translate to better patient satisfaction is what this study aims to see. The study is restricted to patients undergoing Head & Neck procedures under General Anaesthesia, as they form the major bulk of patients in our minor OT complex and for logistic reasons to start with a defined group of patients.

AIMS AND OBJECTIVES:

1. To reduce postponement of cases due to lack of information to patients in the pre-operative period
2. To compare satisfaction levels between patients , pre and post introduction of information leaflet

Primary end point:

To reduce postponement of cases due to lack of information to patients in the pre-operative period

Co Primary end point:

To compare satisfaction levels between patients, pre and post introduction of information leaflet.

Design of the study: Pre and post interventional model

INCLUSION CRITERIA:

All adult patients (> 18yrs), ASA I-III, undergoing elective therapeutic/diagnostic Head & Neck surgeries under General Anaesthesia in the Minor OT complex and discharged on the same day will be included. The surgeries will include Head & Neck surgeries like DL scopes, laser surgeries, EUA, excision biopsies etc.

EXCLUSION CRITERIA:

1. Patients refusing to take part in study
2. Patients undergoing emergency surgeries
3. ASA IV patients, or high risk patients planned for admission
4. Admitted patients for minor OT procedure
5. Patients not getting the Information leaflet due to any reason (in 2nd half of study)
6. Patient and his attendant, both illiterate

MATERIAL AND METHODS

After Institutional Review Board approval, all adult patients meeting inclusion criteria and undergoing surgeries in the Minor OT complex during a 6 month period will be enrolled in the study. The study will be done in two parts.

In the First half of study- planned over 2 months (Nov-Dec), feedback forms will be collected from patients at the end of minor OT procedure (Annexure 2.1) All patients, meeting inclusion criteria, at the end of the procedure prior to discharge from the minor OT will be explained about the study and they shall be given a feedback form to be filled and submitted. Also the number of postponement or rescheduling of cases will be noted.

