Postponement or rescheduling of case is defined as an event when the patient who is called for his turn in minor OT is deferred for any amount of time in account of starvation not adequate, investigations not brought, medications not taken as prescribed. Any postponement in view of awaiting opinion from senior consultant , special equipment or any investigations called in view of patients clinical conditions which was not anticipated in the OPD by the surgical colleague, or due to lack of OT time will not be included.

After the initial collection of feedback over 2 months, the patient information leaflet (PIL) will be handed over to all patients planned for procedure in the minor OT complex (Second half of study). This leaflet will be handed over by the attending doctor in the Head neck OPD. The checklist pertaining to counselling at the Head neck OPD will be ticked after they are carried out. The patient will be instructed to read leaflet carefully and carry the leaflet on the day of Minor OT procedure. In the minor OT the discharge checklist in the PIL would be carried out by all concerned including the surgical, anesthesia and nursing team. A period of 1 month (Jan) will be allowed to streamline the use of patient information leaflet.

In the subsequent 2 months, Feb - Mar, the impact of use of PIL will be assessed. Firstly by noting the number of postponement or rescheduling of cases. In addition all patients meeting inclusion criteria will be given the feedback form (Annexure 2.2) at the end of their procedure in minor OT.

For patients coming to minor OT without a patient information leaflet- one would ascertain if the leaflet was handed in OPD and not brought to minor OT or if the leaflet was not handed at all. The numbers of such misses will be recorded. Patients who did not get the leaflet in the OPD will be excluded from study.

Sample size calculation:

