5. Were you adequately informed with regard to the fasting procedure, pre-surgery (What to eat/drink)?

Yes No Not sure

6. Were you informed about any tests (blood tests, ecg, scans,x-ray etc.) that were necessary before the procedure?

Yes No Not sure

7. If you take any medicine on a regular basis, were you informed about which medicines to continue or to avoid on the day of surgery?

Yes No Not sure

8. Did you receive enough information about the future course of action about your treatment (includes when to expect the result of today's procedure, future treatment & follow up)

Yes No Not sure

9. Have you received any Information leaflet at the OPD?

Yes No

If "yes "have you read the leaflet?

Yes No

If "yes "have you understood the information provided in the leaflet?

Yes No

10. What is your opinion about the leaflet?

Very Good Good Average Bad Very Bad

11. Would you recommend this leaflet to others?

Strongly recommend / will Recommend/ Neutral /recommend reluctantly/ not recommend at all

12. How was your overall satisfaction with respect to the information you were provided before the surgery?

Excellent Very good Good Poor Very Poor

13. How was your overall satisfaction with respect to the information you were provided after the surgery?

Excellent Very good Good Poor Very Poor

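### Only the after-period form asks patients to judge the leaflet before they rate satisfaction, so question order is confounded with period for the co-primary endpoint

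*Combined protocol and SAP*

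**What the plan says.** The Aims and Objectives include "To compare satisfaction levels between patients , pre and post introduction of information leaflet", and the same comparison is listed as the co-primary end point.

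Material and Methods assigns one form to each period. In the first half, "feedback forms will be collected from patients at the end of minor OT procedure (Annexure 2.1"), and patients complete it themselves: "they shall be given a feedback form to be filled and submitted". In the second half, eligible patients "will be given the feedback form (Annexure 2.2) at the end of their procedure in minor OT".

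Both forms end with the same two satisfaction items, with identical wording and five response options: "How was your overall satisfaction with respect to the information you were provided before the surgery" and "How was your overall satisfaction with respect to the information you were provided after the surgery". They are items 9 and 10 on Annexure 2.1, and items 12 and 13 on Annexure 2.2. The gap on Annexure 2.2 is filled by leaflet questions: item 9 (received, read, understood), item 10 ("What is your opinion about the leaflet") and item 11 ("Would you recommend this leaflet to others").

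The Statistical Analysis section treats Likert scores as ordinal, compares proportions by chi-square, and names age, sex and patient knowledge as covariates for satisfaction. It does not mention form version or question order.

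**The concern.** A comparison of ratings between periods needs the same measurement in both. Here, only after-period patients are asked to rate the leaflet and say whether they would recommend it immediately before they rate the information they received. A patient who has just endorsed, or criticised, the leaflet may carry that judgement into the next answer.

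Item 12 is the likeliest place. It follows item 11 directly and concerns pre-surgery information, which the leaflet handed out in the OPD is meant to supply. Item 13 is less exposed: it follows item 12, just as item 10 follows item 9 on the before form. It is not immune, because the leaflet also carries a discharge checklist.

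Upward carry-over could make an ineffective leaflet look effective. Downward carry-over could hide a real benefit, or create an apparent worsening.

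**Working it through.** **1. The forms side by side**

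| Content | Annexure 2.1 (before) | Annexure 2.2 (after) |
|---|---|---|
| Demographics, previous visit, information received | items 1-8 | items 1-8, same questions |
| Leaflet received / read / understood | none | item 9 |
| Opinion of leaflet | none | item 10 |
| Would recommend leaflet | none | item 11 |
| Satisfaction, information before surgery | item 9 | item 12 |
| Satisfaction, information after surgery | item 10 | item 13 |

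No leaflet question precedes satisfaction on the before form. On the after form three numbered items do, or five questions counting sub-questions.

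**2. Why analysis cannot resolve it**

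The expected difference between periods is (leaflet effect) + (order effect) + (other period differences). Every before-period patient has one order and every after-period patient the other, so form version does not vary within a period. The data give one difference and cannot split it. Adjusting for age, sex and patient knowledge leaves this unchanged, as would any other covariate.

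**3. The plan's own sample size**

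This concerns postponement only; no sample size or power is stated for satisfaction. With rates 0.20 and 0.10, pooled rate 0.15, two-sided alpha 0.05 and power 0.80:

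n = [1.960·√(2·0.15·0.85) + 0.8416·√(0.20·0.80 + 0.10·0.90)]² / 0.10² = (0.98974 + 0.42081)² / 0.01 = 198.97, so 199 per group. Power at 199 is 0.80007. The stated figures reproduce, and 199 per group is used below.

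**4. How large could it be? (all inputs assumed)**

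The documents give no satisfaction distribution and no order effect. The illustration takes one satisfaction item and three assumed before-period distributions, from very poor to excellent:

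- A: 0.03 / 0.10 / 0.37 / 0.32 / 0.18
- B: 0.01 / 0.04 / 0.20 / 0.35 / 0.40
- C: 0.10 / 0.20 / 0.40 / 0.20 / 0.10

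There is no true effect. A share s of each of the lower four categories moves up one level in the after period. Each setting has 100,000 simulated studies, tested two-sided at 0.05 by a 5×2 chi-square and by a Wilcoxon-Mann-Whitney test with tie correction. Entries are the proportion significant, chi-square / rank test.

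| Distribution | s = 0 | s = 0.05 | s = 0.10 | s = 0.20 |
|---|---|---|---|---|
| A | 0.050 / 0.051 | 0.059 / 0.071 | 0.092 / 0.134 | 0.257 / 0.393 |
| B | 0.044 / 0.050 | 0.050 / 0.064 | 0.070 / 0.108 | 0.171 / 0.291 |
| C | 0.049 / 0.051 | 0.059 / 0.068 | 0.092 / 0.126 | 0.253 / 0.368 |

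As a share of all patients, s = 0.05, 0.10 and 0.20 means 4.1%, 8.2% and 16.4% under A (0.82 × s), 3%, 6% and 12% under B (0.60 × s), and 4.5%, 9% and 18% under C (0.90 × s).

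Check by formula for A, s = 0.10: the after distribution is 0.027 / 0.093 / 0.343 / 0.325 / 0.212. The noncentrality is 199 × Σ(p − q)²/(p + q) = 0.813, which on 4 degrees of freedom gives 0.094, in line with the simulated 0.092.

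**5. Downward carry-over (distribution A only)**

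- *No true effect.* Moving 5%, 10% or 20% of the upper four categories down one level gives a significant result in 0.062, 0.113 and 0.345 of studies (chi-square) or 0.074, 0.147 and 0.437 (rank test). These are false apparent worsenings.
- *A real benefit, partly hidden.* Assume one third of those below the top category truly improve by one level (0.82/3 = 27.3% of all), giving 0.0200 / 0.0767 / 0.2800 / 0.3367 / 0.2867. Detection in favour of the after period is 0.805 (rank test) or 0.635 (chi-square). Adding downward carry-over of 5%, 10% or 20% lowers it to 0.647, 0.465 and 0.153 (rank test) or 0.500, 0.394 and 0.245 (chi-square).

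**The case against.** The strongest reply is that the documents show a difference in order, not that order changes answers. They also give reasons to expect little extra effect. Patients are told to read the leaflet and bring it, and staff complete its checklist in the minor OT that day, so most have it in mind before they see the form. Items 5-8 already direct attention to fasting, tests, medicines and follow-up on both forms. Recalling the leaflet is a proper part of answering item 12; only carry-over beyond that is bias, and nothing isolates it. The illustration rests on invented shifts. With chi-square, the only comparison test the plan names, 5-10% upward carry-over gives about 5-9% against a nominal 5%, and no text suggests downward carry-over. Finally, a before/after comparison among patients who know they received a leaflet would stay confounded after reordering.

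Most of this stands as a limit on size and priority. It does not remove the point. Having a leaflet in hand differs from being asked to rate and recommend it just before the outcome question, and that prompt comes from the form, in one period only. Confounding by calendar period comes with the chosen design; this confound does not, and it can be reduced without changing the design.

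**Conclusion.** The concern holds. Question order is fully confounded with period for the co-primary satisfaction comparison, and neither the documents nor any analysis of the planned data can separate the two.

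The size and direction are unknown. Under the stated assumptions, carry-over in 5% of those who could move does little harm to the false-positive rate. At 20% the effect is material: 17-26% false positives by chi-square and 29-39% by rank test for an upward shift. Nothing in the documents shows which size, if any, applies. The change should be made because it is cheap and the asymmetry is avoidable, not because bias has been shown. Postponement does not use the form and is unaffected.

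**What to change.** On Annexure 2.2, place the two satisfaction items directly after item 8, as items 9-10, to match Annexure 2.1. Move the leaflet items (now 9-11) to the end as items 11-13. If the after-period form is already in use, do not change it midway; state the order difference as a limitation of the satisfaction comparison.

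The cost is renumbering one form, and resubmitting it if already approved. No question is added and the sample size is unchanged. There are three caveats:

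- Respondents complete the form themselves and can read ahead, so reordering reduces carry-over but may not remove it.
- Satisfaction ratings may then influence the leaflet answers. Those appear on one form only and are not compared between periods. However, the patient knowledge covariate is undefined; if it is to draw on the read and understood questions, those answers would now follow the ratings.
- The period, selection and awareness limits of a before/after design remain.
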